Cover page

Title: Neuromodulation Using Vagus Nerve Stimulation Following Ischemic Stroke as

Therapeutic Adjunct (NUVISTA)

NCT number: NCT05390580, Approval Date: 2/4/2025

Study Title: Vagus Nerve Stimulation following a Large Vessel Occlusion Acute Ischemic Stroke

(NUVISTA)

Principal Investigator: [name] MD

Co-investigator(s): [name] [name]; [name] MD

Sponsor or funding source: None

Objectives

To quantify inflammatory markers in the blood of patients who present with ischemic strokes due to large vessel occlusions to Barnes Jewish Hospital, and determine if treatment with auricular transcutaneous vagal nerve stimulation alters the levels of inflammatory markers in these patients over time, and we will explore if it impacts their overall outcome.

Methods and Measures

Design

This is a randomized open-label, with blinded outcome pilot study to evaluate the effect on inflammatory laboratory values and explore clinical outcomes in patients who present with ischemic strokes due to large vessel occlusions and are treated with either current accepted management, or accepted management in addition to transcutaneous auricular vagal nerve stimulation.

Setting

Patients in this study will be inpatient at Barnes Jewish Hospital

Data Collection Criteria

Adult patients who present with acute ischemic strokes due to large vessel occlusions to Barnes Jewish Hospital will be considered for enrollment in this study. Exclusion criteria will include patients <18 years old, patients with presumed chronic large vessel occlusions, posterior circulation LVOs, NIHSS<6, CTP Penumbra <1/3 total ischemic area, pre-morbid modified Rankin score (mRS) >2, unable to initiate treatment under 36 hours from symptom discovery, life expectancy <3 months, patients' undergoing active cancer or immunosuppressive/modulating therapy, or patients with sustained bradycardia on arrival with a heart rate <50 beats per minute.

Sample size

We anticipate enrolling approximately 80 patients into the study, with random assortment to treatment with standard medical care, and standard medical care with transcutaneous auricular vagal nerve stimulation.

Intervention

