Patients enrolled in the trial will be randomized to treatment with or without electrical stimulation via an auricular, transcutaneous vagus nerve stimulator. All patients will be fitted with the device, we will attach adhesive contacts to the left ear. Stimulation sessions will occur for 20 minutes twice daily during the inpatient period. Patients assigned to the controls arm will have no electricity applied,

those treated with stimulation will be treated with the following parameters: frequency 20 Hz, pulse width 250 μ m, and varying intensities from 0.4 mA to 2 mA (intensity is always titrated to be a level below painful threshold in a patient). The amplitude of stimulation may be reduced if a patient complains of discomfort at the site of stimulation. The site of stimulation will be inspected daily before and after treatment to ensure there is no redness or irritation at the site.

Outcome Measure(s)

The primary endpoints of the study will be changes in the levels of inflammatory markers that include IL-1b, IL-6, TNF-α, and white blood cell count in the blood, as well as specific inflammatory cell counts (neutrophil to lymphocyte ratio, for example) at time of admission, and every day throughout the hospitalization. The secondary exploratory endpoints will be clinical outcomes assessed via the change in daily NIHSS and mRS at 30 and 90 days, as well as safety endpoints with regards to blood pressure and heart rate. We will also do mononuclear cell genetic testing to attempt to identify phenotypes that respond to the intervention. Follow up data will be obtained via chart review, we will obtain the mRS data at 30 days over the phone, and we will make additional outpatient follow up appointments for the research study in order to collect the NIHSS and mRS data at 90 days.

Analytical Plan

Results will be analyzed initially using descriptive statistics. Comparison between groups will be done using chi square tests for proportions, and t-tests or ANOVA procedures for continuous variables. Regression analysis will be performed to identify independent outcome predictors. Other inferential statistical analysis will be conducted as appropriate. Please see document with statistical plan that is attached.

Human Subjects Protection

Subject Recruitment Methods

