Statistical analyses were performed using Stata/MP version 18 (StataCorp LLC 2023, Statistical Software, College Station, TX) and Python packages Scipy and Statsmodels. All continuous variables were retained as continuous, except where noted. Multivariable regression was used to examine treatment group associations with outcomes, except for rare secondary outcomes/adverse effects. Following FDA recommendations, an intention-to-treat (ITT) approach was implemented. Primary ITT analyses were conducted without transformation of continuous outcome variables because ≥35 observations were available.

Statistical analysis of rate of change in cytokines, WBC, and neurological outcomes in taVNS vs. sham treatment.

Longitudinal data were analyzed using mixed effects models per the FDA, with person as a random effect, given multiple records per person. For cytokine models, assay plate was included as an additional random effect. This approach accommodated irregularly timed points, less restrictive missing data assumptions, and time-varying variables. To complement our primary ITT approach, treatment also was handled as time-varying when noted, with assignment occurring at randomization. All longitudinal models included treatment, time since LKN, and their interaction term(s) as primary independent variables to test whether the pattern of change over time differed between the taVNS and sham groups. Time was modeled quadratically for cytokine and WBC outcomes to capture the known U-shaped associations with time when modeling these outcomes and linearly for in-hospital NIHSS scores based on panel data plots. For NIHSS, a single model was constructed to estimate the rate of change (change in NIHSS per

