day) in each of the two treatment groups and to formally test whether these rates were different. For 30-day NIHSS changes (vs. baseline) and 90-day mRS changes, we used the parallel model, with actual assessment days scaled to standardize the evaluation period to 30 or 90 days, respectively. We characterized the daily change in each WBC or cytokine outcome using a similar model expanded to include the quadratic terms. Treatment-time interactions were tested using likelihood ratio tests comparing models with and without interaction term (NIHSS, mRS) or terms (cytokines, WBC), with significance at two-sided α =0.05. These analyses were adjusted for baseline covariates, including baseline NIHSS (except in NIHSS models, which included this observation), time from LKN to thrombus removal time or recanalization attempt (groin puncture time), and percent reperfusion (0-100%) based on TICI score to obtain a single semicontinuous measure. In sensitivity analyses, we also performed the analysis with a dichotomized TICI scale (reperfused ≥2B, not reperfused <2B) or restricted data to the first five days post-LKN (when most stimulations and hospitalizations had ended). Finally, we explored whether any difference in longitudinal patterns between taVNS and sham depended any of the a priori adjustment variables, i.e., whether any time-treatment interaction depended on one of these three variables. We conducted post-hoc t-tests to compare cytokine levels between groups on each day.

Statistical analysis of safety and exploratory analysis of the Stroke Complications and Poor Outcomes in relation to treatment.

To assess our dichotomous safety endpoints, we used logistic regression models constructed to assess differences in bradycardia, hypotension, infection, hemicraniectomy, hemorrhagic transformation, and deaths amongst treated vs non-treated patients. To explore the hypothesis that taVNS reduces the incidence of complications and poor outcomes, we performed logistic

regression models for discharge related outcomes, defined as: readmission, length of stay, and hospital poor disposition (i.e. nursing home, long-term acute care hospital, or death).

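### Length of stay is assigned to logistic regression without a cut-point or ordered categories, and the plan does not say how an in-hospital death counts in it (minor, exploratory outcome)

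*Combined protocol and SAP*

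**What the plan says.** Length of stay appears once in the documents, in the last subsection of the Expanded Statistical Analysis (safety, complications and poor outcomes). The purpose there is stated as "To explore the hypothesis that taVNS reduces the incidence of complications and poor outcomes", and the method is logistic "regression models for discharge related outcomes, defined as: readmission, length of stay, and hospital poor disposition". Disposition is spelled out as "poor disposition (i.e. nursing home, long-term acute care hospital, or death"; length of stay is not defined further.

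Three other places bear on the point:

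- The opening of the Expanded Statistical Analysis: "All continuous variables were retained as continuous, except where noted".
- The protocol's Analytical Plan: "t-tests or ANOVA procedures for continuous variables".
- The sensitivity analyses, where a split is used and its threshold is written out: "dichotomized TICI scale (reperfused ≥2B, not reperfused <2B".

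Death is also a separate dichotomous safety endpoint. Nothing links it to length of stay.

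**The concern.** Binary logistic regression needs a yes/no outcome. Without a threshold, an analyst cannot run the length-of-stay model as written, and a reader of the resulting odds ratio cannot tell what it compares. Splitting a duration also discards information, which a pilot with about 40 patients per arm can ill afford.

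The second gap is independent of the first. Whatever the model, the length of stay of a patient who dies in hospital has to be coded somehow. Taken at face value, a death before the threshold is a short stay and a death after it is a long one. The first coding credits an arm with a good result for an event that the same sentence counts as poor. If mortality differs between arms, the length-of-stay comparison then moves even when survivors do not differ at all.

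**Working it through.** The documents state no power, event rate or effect size for length of stay, so there is no figure to reproduce. **From the documents:** total sample size, "We anticipate enrolling approximately 80 patients into the study"; and a remark that guides the assumed stay, "restricted data to the first five days post-LKN (when most stimulations and hospitalizations had ended". **Assumed:** 1:1 allocation (40 per arm), 40–45% of survivors staying beyond day 5, in-hospital mortality, timing of deaths, and the shape of the stay distribution. The remark about five days says nothing about when deaths occur.

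**1. Effect of the unstated death coding.** Let d be the proportion dying in hospital, s the proportion of survivors staying beyond the cut-point, and f the share of deaths falling after it. Under observed-stay coding:

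P(long stay) = (1 − d)·s + d·f

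With s = 0.45 in both arms and d = 0.10 v 0.20:

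- f = 0: 0.90 × 0.45 = 40.5% v 0.80 × 0.45 = 36.0%. Odds ratio = (0.360/0.640)/(0.405/0.595) = 0.83.
- f = 0.45 (deaths timed like discharges): 45.0% v 45.0%. Odds ratio 1.00.
- f = 1: 50.5% v 56.0%. Odds ratio = (0.560/0.440)/(0.505/0.495) = 1.25.

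The range over s = 0.40 and 0.45, for the arm with more deaths:

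| Deaths | All before cut | Timed like discharges | All after cut |
|---|---|---|---|
| 10% v 15% | 0.91–0.92 | 1.00 | 1.12–1.13 |
| 10% v 20% | 0.83–0.84 | 1.00 | 1.25–1.27 |
| 5% v 20% | 0.75–0.77 | 1.00 | 1.39–1.44 |

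Excluding deaths also gives 1.00.

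**2. Sampling error.** For the 0.83 case with 40 per arm, the expected cell counts are 16.2, 23.8, 14.4 and 25.6. SE(log OR) = √(1/16.2 + 1/23.8 + 1/14.4 + 1/25.6) = 0.461, so the 95% interval is 0.33 to 2.04. For the 1.25 case it is 0.52 to 3.01.

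**3. Death ranked worst.** With identical survivors, the chance that a patient in the higher-death arm (d₁) fares better than one in the other arm (d₀), counting ties as half, is

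(1 − d₁)d₀ + ½(1 − d₁)(1 − d₀) + ½d₀d₁

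For 20% v 10%: 0.08 + 0.36 + 0.01 = 0.45, whenever the deaths occur. The direction no longer depends on timing.

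**4. Cost of splitting.** Simulation (40,000 trials per setting): lognormal stay with median 5 days, rounded to whole days, log-SD 0.6 to 0.8; survivors' median 30% shorter in one arm; deaths equal in both arms and counted as unfavourable under both methods; two-sided 5%; both tests unadjusted.

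| Deaths in each arm | Rank test power | Day-5 split power | Gain (points) |
|---|---|---|---|
| 0% | 48–72% | 35–54% | 13 to 19 |
| 10% | 34–53% | 28–42% | 5 to 11 |
| 20% | 23–36% | 24–35% | −1 to +1 |

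**The case against.** **The passages do not strictly contradict each other.** The general rule allows noted exceptions, and listing length of stay under logistic regression could be read as one whose threshold was left out. The Analytical Plan is a general summary that defers to the attached statistical plan. This stands as far as it goes: a reader might infer a flat contradiction, and the text falls short of one. But a noted exception without a threshold still cannot be run, and calling the model ordinal does not help because no categories are given.

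**A reader might infer an inflated false-positive rate.** Under the null, with the stay distribution above, reporting the best of four cut-points (days 4, 5, 7 and 10) gives a rate of 13–16%. That requires someone to choose the cut by its result, and nothing in the documents indicates this. A single cut fixed in advance holds its level at roughly 5% (4.9–6.1% in a rerun).

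**A reader might infer bias toward stimulation.** The documents give no mortality by arm and no death timing, and the artefact can point either way or vanish.

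**Ranking death worst changes the question.** This stands. With identical survivors and deaths of 10% v 20%, the rank test rejects in 11–12% of trials, against 7–8% for a day-5 split that codes deaths as short stays. Those rejections reflect a real mortality difference, not stay, and the plan already tests death separately. Survivors' stay and deaths must therefore be shown apart.

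**Readmission.** A reader might extend the point to readmission, which has no stated time window. That is missing detail, not a model unsuited to its outcome, and is no part of this point.

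**Conclusion.** The point holds, as a minor one. The stated model does not fit the outcome as described, and no place in the documents settles how an in-hospital death enters length of stay. In the illustrations, the death coding alone moves the odds ratio between 0.75 and 1.44 across the mortality contrasts tried, with no difference among survivors. Those extremes need both a mortality imbalance and all deaths on one side of the cut; with equal mortality or deaths timed like discharges there is no distortion. All of these figures rest on assumed inputs and show direction and order of size only.

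Three things limit the weight. The analysis is exploratory, and length of stay is not among the endpoints under Outcome Measure(s). Death is reported in its own right and within disposition. The primary inflammatory-marker analysis is unaffected.

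**What to change.** Analyse length of stay in days without dichotomising, by proportional-odds (ordinal) logistic regression with in-hospital death as the worst category. Adjust for the baseline covariates that the plan names for its longitudinal models: baseline NIHSS, time from last known normal to thrombus removal or recanalization attempt, and percent reperfusion. This keeps to the plan's stated use of multivariable regression; a Wilcoxon rank test is the unadjusted equivalent. Show beside it, by arm, the stay in survivors and the number of in-hospital deaths.

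The plan is written in the past tense. If the logistic analysis has already been run, report the cut-point and death coding that were used, label the replacement post hoc, and show both.

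The cost is a sentence or two of wording and one re-specified model, with no new data. The downsides are a less familiar effect measure, a measure that mixes mortality with stay, and a power gain that shrinks as mortality rises and is nil at 20%. At that level the case for the change rests on having a defined outcome and a fixed death rule, not on power.

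### The exploratory poor-disposition endpoint is a closed list without hospice, so a patient discharged alive to home or free-standing hospice is coded as not poor

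*Combined protocol and SAP*

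**What the plan says.** The final paragraph of the Expanded Statistical Analysis, on safety and exploratory outcomes, has an openly exploratory aim: to see whether taVNS lowers the frequency of complications and bad results. It names logistic models for this and lists what they cover: "regression models for discharge related outcomes, defined as: readmission, length of stay, and hospital poor disposition". The third of these outcomes is then spelled out as "hospital poor disposition (i.e. nursing home, long-term acute care hospital, or death".

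Death is also analysed as a safety endpoint in the same paragraph ("hemicraniectomy, hemorrhagic transformation, and deaths amongst treated vs non-treated patients"), with no time window given. Outcome Measure(s) adds "clinical outcomes assessed via the change in daily NIHSS and mRS at 30 and 90 days" as secondary exploratory endpoints.

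The Sample size section says "We anticipate enrolling approximately 80 patients into the study" and gives no allocation ratio. The Design section states "This is a randomized open-label, with blinded outcome pilot study".

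**The concern.** The abbreviation i.e. introduces a complete list, not examples. Where the authors mean an example they say so, as Outcome Measure(s) does for the neutrophil to lymphocyte ratio. A logistic model needs two categories, so every destination off the list goes into the reference group. A patient sent home or to a hospice unit for end-of-life care is then grouped with patients who went home recovering. Another patient with the same course who dies on the ward is coded poor.

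Such discharges are plausible here. The Data Collection Criteria exclude "NIHSS<6, CTP Penumbra <1/3 total ischemic area, pre-morbid modified Rankin score (mRS) >2", so participants have at least moderately severe large vessel strokes. The SAP also says that most hospital stays were over within five days of last known normal. The exclusion for life expectancy under 3 months applies at entry and does not prevent a hospice discharge after the stroke evolves.

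At stake is the reading of one of the three discharge outcomes used to explore whether taVNS reduces poor outcomes.

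**Working it through.** **Inputs from the documents.** Three listed destinations; a binary model; about 80 patients. The documents state no event rate, effect size or power for disposition, so there is no figure of the plan's to reproduce.

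**Assumed for illustration.** 1:1 allocation (80/2 = 40 per arm); a true poor-disposition rate p, hospice included, of 30% to 50%; hospice outside a nursing home or long-term acute care hospital at 2.5% to 15%.

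**Step 1: apply the rule as written.**
- Nursing home, long-term acute care hospital, death before discharge: poor.
- Hospice care given inside a nursing home or long-term acute care hospital: poor, because the place is listed.
- Home hospice or free-standing hospice, patient alive at discharge: not poor.

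Hospice, palliative care and comfort care are not mentioned anywhere, so no other rule changes the third line.

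**Step 2: size of one misclassification.** 1/40 = 2.5 percentage points of an arm's rate. Across 80 patients, 2.5% to 15% is 80 × 0.025 = 2 to 80 × 0.15 = 12 patients.

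**Step 3: effect on the odds ratio when there is no true effect.** Recorded OR = odds(p − h_taVNS) / odds(p − h_sham), where odds(x) = x/(1 − x).

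| Hospice, sham v taVNS | p = 30% | p = 40% | p = 50% |
|---|---|---|---|
| 5% v 5%, or 10% v 10% | 1.00 | 1.00 | 1.00 |
| 5% v 10% | 0.75 | 0.80 | 0.81 |
| 5% v 15% | 0.53 | 0.62 | 0.66 |
| 10% v 5% | 1.33 | 1.26 | 1.23 |

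In counts, for p = 40% and 5% v 10%: 16/40 are truly poor in each arm, with 2 hospice discharges in sham and 4 in taVNS. Recorded poor is 14/40 in sham and 12/40 in taVNS. OR = (12/28)/(14/26) = 0.429/0.538 = 0.80. Counting hospice as poor restores 16/40 v 16/40 and an OR of 1.00.

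**Step 4: equal hospice use.** With no true effect the OR stays at 1.00, but each arm's rate is too low by the hospice rate: at p = 40% and 5% hospice, 35% is recorded. With true rates of 50% (sham) v 30% (taVNS), the OR is (0.30/0.70)/(0.50/0.50) = 0.43. Leaving out 5% in each arm gives (0.25/0.75)/(0.45/0.55) = 0.41, and leaving out 10% gives (0.20/0.80)/(0.40/0.60) = 0.375. Power at 40 per arm is about 45% with hospice counted and 47% to 50% without it. The problem is validity, not power.

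**Step 5: against sampling error.** For 12/40 v 14/40, the standard error of the log OR is √(1/12 + 1/28 + 1/14 + 1/26) = √0.229 = 0.478. The 95% interval is exp(−0.228 ± 1.96 × 0.478), about 0.31 to 2.03. The shift from 1.00 to 0.80 is small beside that width.

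**The case against.** The best case for leaving this alone is that the endpoint is exploratory, in a pilot whose primary endpoints are inflammatory markers, and that any plausible shift is well inside the sampling error. Deaths are analysed separately with no stated restriction to in-hospital death, and mRS is taken at 30 and 90 days, so a patient who dies in hospice may appear there. The SAP text is a short summary in the past tense, and staff may in practice have coded hospice with death. All of this bears on priority. None of it repairs the endpoint: the other outcomes do not alter how disposition is coded, and no text says hospice was grouped with death.

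A reader might infer more than the documents support:
- *That these patients are counted as good outcomes.* The plan defines only poor disposition; the accurate statement is that they are coded not poor.
- *That every hospice patient is missed.* Those in a nursing home or long-term acute care hospital, and those who die before discharge, are captured.
- *That the open label would steer discharges and create a false reduction in poor disposition.* The Intervention section has all patients fitted with the device, with no current in controls, and the SAP calls the comparator sham. The documents do not say whether staff deciding on discharge knew the allocation, and they report no hospice use by arm. An imbalance could arise by chance or otherwise, and in either direction.

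**Conclusion.** The point holds as a defect in one exploratory endpoint. Followed as written, the definition places live discharges to home or free-standing hospice in the not-poor group. Equal use understates the poor-disposition rate; unequal use distorts the odds ratio either way. The actual size cannot be known from the documents. The recorded range of 0.53 to 1.33 under a true odds ratio of 1.00 rests wholly on the assumed rates in the table, and the 2.5 points per patient on an assumed 40 per arm. The primary marker analysis is not touched. It is worth correcting because a stated rule gives the wrong classification and the repair is small.

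**What to change.** Add hospice, at home or in a facility, to the poor-disposition list. Classify each patient's discharge destination from the chart, blind to arm. Fit the logistic model under the revised definition and under the definition as written, and report both. The SAP is written as though the analysis is complete; if it has been run, label the revision post hoc.

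Cost: one line in the SAP, a small recode and one extra model. The reported poor-disposition rate will be slightly higher wherever hospice discharges occurred.
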